2. BACKGROUND

2.1 Urothelial carcinoma of the bladder

Urothelial carcinoma of the bladder is the fifth most common malignancy in the United States, with an estimated 75,000 new cases and 15,000 deaths in a year [1]. Approximately 25% of new cases are muscle-invasive bladder cancer (MIBC), while the rest are non-muscle-invasive bladder cancer (NMIBC). Accurate staging of bladder cancer is paramount in deciding the appropriate course of management. While NMIBC is generally managed by cystoscopic resection with intravesical BCG or chemotherapy, the standard treatment for MIBC is radical cystectomy (RC) preceded by neoadjuvant chemotherapy (NAC) in cisplatin-eligible patients [2-4]. It is estimated that ~30% of patients undergoing RC may have nodal metastases [5, 6]. Metastatic disease has exhibited improved outcomes when treated with first-line systemic cisplatin-based chemotherapy and salvage post-platinum therapy using one of multiple programmed death (PD)-1 and PD-ligand (L)-1 inhibitors (pembrolizumab, atezolizumab, durvalumab, nivolumab, avelumab) [7-13]. Additionally, pembrolizumab and atezolizumab are approved for the first-line therapy of cisplatin-ineligible patients based on durable responses [14, 15]. Therefore, pre-operative identification of those with node-positive metastatic disease will enhance prognostic risk stratification and tailoring of neoadjuvant therapy, for example with the consideration of clinical trials of more aggressive and promising neoadjuvant combination

regimens and tailoring the extent of lymph node dissection based on the extent of node-positive disease.

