2.2 Current imaging methods to stage bladder cancer

Current imaging methods used to stage bladder cancer predominantly include computed tomography (CT) and magnetic resonance imaging (MRI). While both are useful in locoregional staging, both exhibit limitations. CT and MRI rely on nodal enlargement as an indicator of disease involvement. Non-enlarged lymph nodes harboring disease can be falsely negative by anatomic imaging. Conversely, false positive lymphadenopathy from benign etiologies can preclude eligible patients from RC. CT and MRI sensitivity for detection of nodal metastasis ranges from 31-50% and specificity ranges from 68-100% [6]. Some reports suggest that 40% of those with bladder confined disease by imaging have extravesical and/or pathologically node-positive disease at RC [16-20].

Fluorodeoxyglucose (¹⁸FDG)-positron emission tomography (PET) is a functional imaging modality that has excellent sensitivity for detecting metastatic disease when combined with anatomic CT or MRI [21-25]. However, effective use of FDG-PET/CT in bladder cancer is limited by the fact that FDG is excreted in urine. Saturation of the imaging signal from within the bladder and urinary tract can affect accurate assessment of locoregional FDG uptake. Furthermore, elevated FDG uptake can also be seen in benign inflammatory conditions and within the gastrointestinal tract, which can also confound staging assessment. Correspondingly, FDG-PET is not approved by regulatory agencies to stage bladder cancer [4].

Given the limitations of both conventional structural CT/MRI and FDG-PET to stage urinary tract cancers, an alternative functional imaging marker without these limitations is highly desirable and warrants investigation.

2.3 ¹⁸Fluorine-Fluciclovine

Anti-1-amino-3-F-18-fluorocyclobutane-1-carboxylic acid (FACBC or ¹⁸F-fluciclovine) is a novel radiotracer for imaging amino acid transporters, which can be over-expressed in cancer [26]. ¹⁸F-fluciclovine was recently approved by the Food and Drug Administration for the detection of biochemically recurrent prostate cancer [27, 28] and it may have a role in complementing MRI for staging localized prostate cancer [29] and radiation planning [30]. ¹⁸F-fluciclovine is predominantly transported in cells via the L-system amino acid transporters, ASCT (alanine-serine-cysteine transporters)-2 and LAT (large neutral amino acid transporters)-1, with peak uptake in tumors 5 to 20 minutes after injection.

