3. PARTICIPANT SELECTION

3.1 Eligibility Criteria

Participants must meet the following criteria on screening examination to be eligible to participate in the study:

- 3.1.1 Participants must have histologically or cytologically confirmed urothelial carcinoma of the bladder.
- 3.1.2 Participants must have cT2-T4N0 disease at the time of the study, as defined by conventional CT or MRI imaging. Patients must have no definite evidence of locoregional or distant metastatic disease at the time of study eligibility, as defined by conventional imaging.
- 3.1.3 Radical cystectomy must be planned for the patient after the planned ¹⁸F-fluciclovine-PET/CT.
- 3.1.4 Patients may or may not have had prior neoadjuvant therapy prior to this study.
- 3.1.5 Age ≥ 18 years. Since no dosing or adverse event data are currently available on the use of ¹⁸F-fluciclovine in participants <18 years of age, and the majority of bladder cancer occur in the adult population [42], children are excluded from this study but will be eligible for future pediatric trials.
- 3.1.6 ECOG performance status ≤ 2 (Karnofsky $\geq 60\%$, see Appendix A)
- 3.1.7 Ability and willingness to comply with the study procedures.
- 3.1.8 The effects of ¹⁸F-fluciclovine on the developing human fetus are unknown. For this reason and because radiopharmaceuticals may be teratogenic, women of childbearing potential and men must agree to use adequate contraception (barrier method of birth control; abstinence) prior to study entry and for 24 hours after the PET/CT scan is completed. Should a woman become pregnant or suspect she is pregnant while participating in this study, she should inform her treating physician immediately.
- 3.1.9 Ability to understand and the willingness to sign a written informed consent document

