5. IMAGING PLAN

5.1 Summary

All procedures will be performed on an outpatient basis. Expected toxicities and potential risks are described in Section 6 (Expected Toxicities and Dosing Delays/Dose Modification).

This is a pilot study investigating ¹⁸F-fluciclovine PET/CT for imaging patients with muscle invasive bladder cancer. The investigational imaging procedure in this study is ¹⁸F-fluciclovine-PET/CT.

After the participant meets eligibility criteria for the study and informed written consent is obtained, the participant will undergo the study procedure (¹⁸F-fluciclovine-PET/CT imaging). ¹⁸F-fluciclovine-PET/CT will be obtained within 6 weeks of the standard-of-care diagnostic staging procedures (MRI and/or diagnostic CT).

Participants will then undergo radical cystectomy per standard-of-care as determined by the medical oncologist. At the time of radical cystectomy, which usually includes pelvic lymph node dissection, standard evaluation of the surgical specimen will determine pathologic staging. We will assess the results of the standard evaluation of the surgical specimen for metastatic disease. These results will be compared with staging as determined by ¹⁸F-fluciclovine PET/CT and standard-of-care diagnostic imaging.

The participant will have completed all study requirements once tissue is obtained at radical cystectomy.

5.2 ¹⁸F-fluciclovine PET/CT imaging

5.2.1 The ¹⁸F-fluciclovine-PET/CT imaging procedure is described in Section 5.4.

Participants will be instructed to refrain from strenuous exercise for the 24 hours preceding the PET/CT exam, since amino acid transporters expression have been

noted to increase in skeletal muscle for that period after exercise [43]. Participants will be NPO for 4 hours prior to administration of ¹⁸F-fluciclovine.

5.2.2 Participants will be provided with instructions regarding what precautions to take at home once they receive the study agent. As with all radiopharmaceuticals administered, participants will receive a card stating that they have received a radiopharmaceutical for medical purposes which includes, but is not limited to, radiopharmaceutical, dosage, suggested time of detection, suggested contamination item storage duration, and institutional and departmental contact information.

Given the short half-life and diagnostic dose of ¹⁸F-fluciclovine (110 minutes), no special precautions regarding excreta or contact with other humans are necessary.

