11.1 Pathological staging of bladder cancer

Pathological staging of bladder cancer is not the primary objective of this study. It will be used for comparison and correlation with imaged-based staging on ¹⁸F-fluciclovine PET/CT and standard-of-care MRI and diagnostic CT.

DATA REPORTING / REGULATORY REQUIREMENTS

Adverse event lists, guidelines, and instructions for AE reporting can be found in Section 7.0 (Adverse Events: List and Reporting Requirements).

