13. STATISTICAL CONSIDERATIONS

13.1 Study Design, Objectives, and Endpoints

This is a prospective pilot study evaluating ¹⁸F-fluciclovine-PET/CT for detecting metastatic disease in patients with cT2-T4N0M0 muscle invasive bladder cancer.

The primary objective of this study is to estimate the agreement rate of metastatic disease status between ¹⁸F-fluciclovine-PET/CT and histopathology from radical cystectomy for detecting

locoregional metastatic disease in patients with cT2-T4N0M0 muscle invasive bladder cancer by conventional CT/MRI imaging. Secondary objectives include estimating of the rate of detection of suspected distant metastatic disease by ¹⁸F-fluciclovine-PET/CT, analysis of the association of ¹⁸F-fluciclovine uptake on PE/CT in primary bladder tumor with pathologic tumor grade/size after radical cystectomy, and analysis of ¹⁸F-fluciclovine uptake on PET/CT to the presence/absence of ASCT2 and LAT1 amino acid transporters in the resected primary bladder tumors.

The primary endpoints are metastatic disease status by ¹⁸F-fluciclovine-PET/CT and pathologic stage at radical cystectomy. The agreement rate is defined as the number of scans that are considered positive metastatic disease by both ¹⁸F-fluciclovine-PET/CT and histopathology and those considered negative metastatic disease by both ¹⁸F-fluciclovine-PET/CT and histopathology, out of all scans performed. A positive ¹⁸F-fluciclovine-PET/CT is defined as evidence of metastatic disease either regionally in the pelvic lymph nodes or distantly to bone, lungs, viscera, or lymph nodes outside of the pelvis. The ability of ¹⁸F-fluciclovine-PET/CT for detecting locoregional metastatic disease will be defined as the presence of disease detected locoregionally on ¹⁸F-fluciclovine-PET/CT. Secondary endpoints include visualization (present/absent) and number of distant metastases on ¹⁸F-fluciclovine-PET/CT. The amount of ¹⁸F-fluciclovine accumulation in the primary bladder tumor on PET will be quantified using the maximum standardized uptake value (SUVmax). Tumor grade/size and the presence of amino acid transporters will be assessed histopathologically with specimens from cystectomy as part of standard-of-care.

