13.3 Sample Size, Accrual Rate and Study Duration

The planned sample size is 16 participants with completed ¹⁸F-fluciclovine-PET/CT scans and pathology dissection. Patients who did not complete the scans or without pathology dissection are unevaluable and will be replaced. Considering 4 patients who may be unevaluable and replaced, up to 20 patients can be enrolled. The estimated accrual rate is 1 participant/month, and accrual is expected to complete in another 16 months. Participants who undergo ¹⁸F-fluciclovine-PET/CT but have altered surgical plans due to clinical findings during surgery may remain evaluable and not replaced if a lymph node dissection was performed as determined by the study investigators. This will not affect the primary study objective given the primary objective is the agreement rate between PET/CT and pathology for metastases. Participants who do not undergo cystectomy will not be included for secondary objectives (2 and 3).

We will employ a Simon's 2-stage design to test the hypothesis that the agreement rate of metastatic disease status between ¹⁸F-fluciclovine-PET/CT and histopathology will be 75%, compared to a null agreement rate of 50%. In the first stage we will enroll 10 patients, and if 6 or more scans among those 10 are in agreement regarding metastatic disease status, we will open the second stage of accrual to enroll an additional 6 patients, making a total sample size of 16 patients. If fewer than 6 scans are in agreement in the first stage then the study may be stopped or the study design may be amended to enroll additional patients. In order to consider the study a success, a total of 11 or more scans need to be in agreement among all 16 scans. This design has a 0.62 probability of stopping early under the null, and has 79.9% power while maintaining an overall one-sided type I error rate of 0.101. The agreement rate between ¹⁸F-fluciclovine-PET/CT and histopathology is expected to be 75% (or higher) and the corresponding 90% CI will be (0.52, 0.91).

| Accrual Targets | | | |
|---|------------|--------|-------|
| Ethnic Category | Sex/Gender | | |
| | Females | Males | Total |
| Hispanic or Latino | + | = | = |
| Not Hispanic or Latino | + | = | = |
| Ethnic Category: Total of all subjects | (A1) + | (B1) = | (C1) |
| Racial Category | | | |
| American Indian or Alaskan Native | + | = | = |
| Asian | + | = | = |
| Black or African American | + | = | = |
| Native Hawaiian or other Pacific Islander | + | = | = |

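### The 0.101 type I error is right at 50% agreement, but in a cohort that is all N0 on CT/MRI a scan read negative in everyone would meet the 11/16 rule with probability about 0.65

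*Combined protocol and SAP*

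**What the plan says.** Section 13.3 sets a Simon two-stage design for agreement between PET/CT and "histopathology will be 75%, compared to a null agreement rate of 50"%. Ten patients enter stage 1. If at least 6 scans agree with pathology, 6 more are enrolled, and success is 11 or more of 16 in agreement. The stated properties are a one-sided type I error of 0.101, power of 79.9%, and a 0.62 probability of stopping early under the null. No reason is given for 50%.

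Four other places bear on what that null means:

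- Section 13.1 counts as agreement the scans positive by both methods and also "those considered negative metastatic disease by both".
- Section 3.1.2 restricts entry by CT/MRI: "Patients must have no definite evidence of locoregional or distant metastatic disease at the time of study eligibility, as defined by conventional imaging".
- Section 2.1 gives the nodal rate: "It is estimated that ~30% of patients undergoing RC may have nodal metastases".
- Section 2.2 gives the accuracy of standard imaging: "CT and MRI sensitivity for detection of nodal metastasis ranges from 31-50% and specificity ranges from 68-100"%. It also cites reports that "40% of those with bladder confined disease by imaging have extravesical and/or pathologically node-positive disease at RC".

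Section 13.2 plans a PET-by-pathology table, the PET-positive proportion with a 90% exact interval, and estimates of sensitivity and specificity. None of these enters the success rule, and no interval is planned for sensitivity or specificity. Section 5.1 says the pathology results will be compared with staging by "PET/CT and standard-of-care diagnostic imaging". Section 11.1 says of pathological staging that "It will be used for comparison and correlation with imaged-based staging on" PET/CT and standard MRI and CT. For locoregional disease, section 13 gives no method for the comparison with standard imaging.

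**The concern.** A null of 50% is natural if an uninformative scan behaves like a coin flip. Here the uninformative comparator is already known: CT/MRI, which is negative in every participant by eligibility. With concordant negatives counted, CT/MRI scores the share of patients who are node-negative at pathology. If 5 of 16 are node-positive, it scores exactly 11/16, which is the success threshold.

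The background motivates the trial by disease that CT/MRI misses. A reader who sees that the study met its success criterion with a type I error of 0.101 may take this as evidence that PET/CT detects such disease. The stated error rate gives no such protection against a scan that rarely reads positive.

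**Working it through.** **Inputs.** The 6/10 and 11/16 rules and the 50% and 75% rates are from 13.3. The nodal rate of about 30% is from 2.1. The 40% and the CT/MRI accuracy ranges are from 2.2. The reader counts are from Appendix B, section 14, Table 4.

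**Formula.** With agreement probability p,

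P(success) = Σ (x = 6 to 10) P[Bin(10, p) = x] × P[Bin(6, p) ≥ 11 − x].

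P(early stop) = P[Bin(10, p) ≤ 5].

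**The plan's own figures.** At p = 0.50, P(success) = 0.1012 and P(early stop) = 0.623. At p = 0.75, P(success) = 0.800. All three match 13.3.

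**A scan read negative in everyone.** It agrees with pathology only in node-negative patients, so p = 1 − v, where v is the node-positive rate. At v = 0.30, p = 0.70, and the terms for x = 6 to 10 are

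0.0841 + 0.1986 + 0.2170 + 0.1197 + 0.0282 = 0.648.

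| Node-positive rate v | Agreement p | P(success) |
|---|---|---|
| 17.6% | 0.824 | 0.946 |
| 20% | 0.80 | 0.911 |
| 25% | 0.75 | 0.800 |
| 30% | 0.70 | 0.648 |
| 40% | 0.60 | 0.320 |

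At v = 0.30, P(early stop) is 0.150, against the stated 0.62. At v = 0.25 the all-negative scan has 75% agreement, which is the design alternative.

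**Which node-positive rate.** The figure of about 30% refers to patients undergoing cystectomy, not to those already selected as N0 on imaging. If 30% is the rate before that selection, the rate among CT/MRI-negative patients is

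v = 0.3(1 − Se) / [0.3(1 − Se) + 0.7 Sp].

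| Se | Sp | v | P(success) |
|---|---|---|---|
| 0.31 | 0.68 | 0.303 | 0.638 |
| 0.50 | 0.68 | 0.240 | 0.827 |
| 0.31 | 1.00 | 0.228 | 0.855 |
| 0.50 | 1.00 | 0.176 | 0.946 |

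The protocol gives Se and Sp as separate ranges, so these pairs are corner cases. The 40% also counts extravesical disease, so it is an upper bound on node-positivity from that source.

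**Readers who call at random.** If a fraction q is called positive without regard to disease, p = vq + (1 − v)(1 − q). At v = 0.30:

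| q | p | P(success) |
|---|---|---|
| 0.1 | 0.66 | 0.512 |
| 0.2 | 0.62 | 0.380 |
| 0.3 | 0.58 | 0.264 |
| 0.5 | 0.50 | 0.101 |
| 0.6 | 0.46 | 0.055 |
| 0.7 | 0.42 | 0.027 |
| 1.0 | 0.30 | 0.0015 |

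So 0.101 describes a coin-flip reader. It understates the pass rate for under-calling and overstates it for over-calling.

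**What the planned analyses would show.** An all-negative scan gives 0/16 PET-positive, with an upper 90% exact limit of 0.17. That would be visible, but it does not affect whether success is declared.

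**Paired difference.** PET/CT agreement is (TP + TN)/16. CT/MRI, negative in all, has agreement (FP + TN)/16. The difference is (TP − FP)/16.

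**The case against.** The strongest reply is that nothing printed is wrong. The 50% null is stated in the same paragraph as the 0.101. The primary objective is to estimate agreement in a pilot, and neither the objective nor the rule claims that success shows detection of disease missed by CT/MRI. Section 13.2 already plans the cross-table, the PET-positive proportion, sensitivity and specificity, and the paired difference can be read off that table. An all-negative reader is an extreme case, made harder to reach because 13.1 also counts any distant site as positive. The only reader data in the documents point the other way: in Table 4, 99/104, 95/105 and 76/99 patients were read positive (95%, 90%, 77%). Random readers at 77% to 95% positive would pass with probability about 0.016 to 0.003 at 30% node-positive.

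Much of this stands. The figures in 13.3 are correct and the all-negative scan is not a forecast. The Table 4 rates are fair counter-evidence, though indirect, since they come from suspected prostate cancer recurrence. It is also true that the 30% is not tied to patients with or without neoadjuvant therapy, both of whom are eligible, and that the calculation equates pathology-positive with node-positive.

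What remains is that 13.3 attaches a formal test, an error rate and a success criterion to agreement alone. The planned analyses that would expose an uninformative scan are not tied to that criterion. The comparison with standard imaging promised in 5.1 and 11.1 has no method for nodal disease.

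**Conclusion.** The concern holds. The 0.101 is right at 50% agreement, but it is not the false-success rate of a scan that adds nothing to CT/MRI. For a scan read negative in everyone that rate is about 0.65 at 30% node-positive, and 0.32 to 0.95 across 40% down to 17.6%. Even the lowest of these is about three times 0.101. CT/MRI itself would meet the rule whenever 5 or fewer of 16 are node-positive and the 6/10 step is met.

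Assumptions: pathology-positive means node-positive; about 30% is the rate before CT/MRI selection; every enrolled patient counts as CT/MRI-negative, including any with equivocal nodes, since 3.1.2 bars only definite evidence; and the stage 1 stop is followed. Section 13.3 leaves that stop optional. Continuing to 16 regardless changes 0.648 to 0.660.

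This should be fixed. It limits what may be concluded from success; it does not invalidate the design.

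**What to change.** Keep n = 16 and both thresholds.

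1. In 13.3, state that 0.101 applies at 50% agreement. Give the all-negative pass rates (0.91, 0.80, 0.65 and 0.32 at 20%, 25%, 30% and 40% node-positive), labelled as assumed rates. Say that 11/16 alone does not show detection of disease missed by CT/MRI.
2. In 13.2, pre-specify that success is reported and interpreted together with the PET-positive proportion, sensitivity and specificity with 90% exact intervals, and the paired difference in agreement, PET/CT minus CT/MRI, as (TP − FP)/16.
3. Record PET pelvic-nodal status (yes/no) separately from distant status, because the three planned categories could place a patient with both only under distant. Compute sensitivity, specificity and the paired difference on the locoregional definition in 13.1. Tabulate distant-only findings separately, and show the difference also under the any-site definition of a positive scan.

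The cost is wording in two sections and one extra field from the same scan, with no added patients or scans. There are downsides. The error protection will look less favourable, and the all-negative pass rate stays at 0.65 because the rule is unchanged. With about 5 node-positive patients (16 × 0.30 = 4.8), sensitivity is imprecise: the 90% exact interval is 0.34 to 0.99 for 4/5 and 0 to 0.45 for 0/5. It can support interpretation but not a test.

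A formal requirement that TP exceed FP would bring the all-negative pass rate to 0. At 30% node-positive and 75% agreement, it would also cut the probability of success from 0.80 to 0.51–0.52 (Se/Sp of 0.50/0.857, 0.60/0.814 and 0.75/0.75). That is a separate trade-off and not part of this change.

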13.4 Stratification Factors

N/A

13.5 Analysis of Primary Endpoints

See section 13.1

13.6 Analysis of Secondary Endpoints

Secondary objectives are to:

1. To determine the rate of detection of suspected distant metastatic disease by ¹⁸F-fluciclovine-PET/CT in patients with cT2-T4N0M0 muscle invasive bladder cancer by conventional CT/MRI imaging.

Endpoints:

- 1) Visualization and number of distant metastases on ¹⁸F-fluciclovine-PET/CT

Visualization of distant metastases on ¹⁸F-fluciclovine-PET/CT will be binary-categorized as present/absent. In the categorization, a qualitative scale (0-4) may be accounted and an optimal cut-off may be examined. We will compute sensitivity to compare ¹⁸F-fluciclovine-PET/CT with standard imaging modalities for distant metastases. The number of distant metastases will be descriptively shown by imaging modalities.

2. To correlate ¹⁸F-fluciclovine uptake on PET/CT in primary bladder tumor with pathologic primary tumor stage and size after radical cystectomy.

Endpoints:

- ¹⁸F-fluciclovine SUVmax in primary bladder tumor
- Primary tumor stage and size at radical cystectomy

The amount of ¹⁸F-fluciclovine accumulation in the primary bladder tumor on PET will be quantified using the maximum standardized uptake value (SUVmax). Tumor grade will be assessed histopathologically with specimens from cystectomy as part of standard-of-care. The correlations between ¹⁸F-fluciclovine uptake and tumor grade will be evaluated using Spearman correlation coefficients.

3. To correlate ¹⁸F-fluciclovine uptake on PET/CT to the presence/absence of ASCT2 and LAT1 amino acid transporters in the resected primary bladder tumors.

Endpoints:

- ¹⁸F-fluciclovine SUVmax in primary bladder tumor
- Presence/absence of ASCT2 and LAT1 amino acid transporter in resected primary bladder tumors

The Wilcoxon-Rank-Sum test will be used to assess the association between SUVmax and the presence/absence of a ASCT2 and LAT1 amino acid transporters in the resected primary bladder tumors.

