5.3 Surgery

After completion of the ¹⁸F-fluciclovine-PET/CT scan, participants will undergo standard-of-care radical cystectomy surgery as determined by medical oncology and urology. If surgical plans (for example, the presence of unsuspected extensive disease precluding cystectomy) are altered based on clinical findings during surgery, the patient may remain evaluable if a lymph node dissection is performed as determined by the study team. Results from the standard-of-care evaluation of the pathologic specimens will be collected and reviewed. This includes evaluation of pathological samples for metastatic cancer burden.

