5.4 Investigational Imaging Agent Administration

10 millicurie (mCi) of ¹⁸F-fluciclovine will be administered via slow push over 10 seconds through a peripheral intravenous line. [33]. This is performed immediately prior to imaging. No specific pre-administration lab parameters or procedures for the patient is required prior to agent administration.

5.4.1 Image Acquisition Details:

Immediately after the injection of the radiopharmaceutical, dynamic PET/CT images of the pelvis will be obtained for 15 minutes. Subsequently, PET/CT images will be obtained from the pelvis to the base of skull in the caudal to cranial direction. CT will be obtained for attenuation correction per standard institutional PET/CT policies. PET images will be acquired in 3D mode at 3-5 minutes per bed position.

As noted in Section 8.1, this image acquisition protocol is based on the pharmacokinetics of the agent in male patients with prostate cancer. While we do not anticipate significant differences in the kinetics of the agent in patients with bladder cancer, appropriate adjustments to the imaging acquisition parameters will be made if significant differences are observed on initial imaging studies.

5.4.2 Image Analysis Details:

¹⁸F-fluciclovine-PET/CT images will be reviewed for lesions, defined as focal areas of ¹⁸F-fluciclovine uptake not correlating with normal anatomy or physiology. Lesions will be scored on a 5-point scale for diagnostic certainty (0, definitely benign; 1, probably benign; 2, equivocal; 3, probably malignant; and 4, definitely malignant).

Three-dimensional regions of interest will be placed in areas of abnormal tracer uptake scored as 3-5 and the level of ¹⁸F-fluciclovine uptake recorded. Measures of ¹⁸F-fluciclovine will include: maximal standardized uptake value (SUV_{max}, body weight), metabolic tumor volume (MTV; volume of tumor [cm³] with SUV >42% of SUV_{max}), SUV_{mean} (within the MTV), and total lesion avidity (TLA; calculated as MTV × SUV_{mean}). Tumor to background ratios will also be calculated using blood pool, muscle and bone marrow as reference normal organs.

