13.2 Data Analysis Plan

The primary and first secondary analyses will include all 16 eligible and treated patients with completed ¹⁸F-fluciclovine-PET/CT scans and pathology dissection. Among these 16 patients, those who undergo cystectomy will be included for secondary analysis 2 and 3.

We will tabulate the metastatic disease status by ¹⁸F-fluciclovine-PET/CT (limited to bladder, locoregional nodes positive, or distant) and pathologic stage at radical cystectomy and compute the agreement rate, along with the corresponding 90% exact binomial confidence interval (CI). The proportion of patients who show positive ¹⁸F-fluciclovine-PET/CT will be computed, along with the corresponding 90% exact binomial confidence interval. This similar methodology will be used to evaluate the proportion of agreement compared to histopathology and the rates of locoregional disease and suspected distant metastatic disease detected by ¹⁸F-fluciclovine-PET/CT. In addition, treating pathologic and/or biopsy findings as the reference standard, we will estimate the sensitivity and specificity of ¹⁸F-fluciclovine-PET/CT for detection of metastatic disease.

The analysis of the relationship of ¹⁸F-fluciclovine uptake on PET/CT (SUVmax) in primary bladder tumor to pathologic tumor grade/size after radical cystectomy will be analyzed using the Kruskal-Wallis test. The Wilcoxon-Rank-Sum test will be used to assess the association between SUVmax and the presence/absence of ASCT2 and LAT1 amino acid transporters in the resected primary bladder tumors.

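### The cut-off that defines distant metastasis as present may be searched on the 16 scans it is reported on, with no distant reference standard scheduled

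*Combined protocol and SAP*

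**What the plan says.** **The endpoint.** Section 13.6, first secondary objective, says that visualization of distant metastases "will be binary-categorized as present/absent". The next sentence reads: "In the categorization, a qualitative scale (0-4) may be accounted and an optimal cut-off may be examined". It gives no optimality criterion, no separate data and no validation, and it does not call the search exploratory. The section then plans an accuracy measure for the same endpoint against standard imaging: "We will compute sensitivity to compare".

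**The analysis set.** Section 13.2 states: "The primary and first secondary analyses will include all 16 eligible and treated patients with completed" scans and pathology. The same section attaches a 90% exact binomial interval to the rate of suspected distant disease.

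**The scale.** Section 5.4.2 says: "Lesions will be scored on a 5-point scale for diagnostic certainty", running from 0 (definitely benign) to 4 (definitely malignant). It does not say which score is positive. Its only numeric rule places regions of interest on "areas of abnormal tracer uptake scored as 3-5", a range that does not fit a scale ending at 4. Section 13.1 defines a positive scan by evidence of metastatic disease, also without a score.

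**The reference.** Section 13.2 plans sensitivity and specificity for metastatic disease, "treating pathologic and/or biopsy findings as the reference standard". On tissue, Section 5.3 says: "Results from the standard-of-care evaluation of the pathologic specimens will be collected and reviewed". Those specimens come from cystectomy and node dissection. Neither Section 5 nor the study calendar schedules a biopsy or confirmatory imaging of a distant lesion. Section 3.1.2 excludes patients with definite distant disease on conventional imaging.

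**The concern.** A present/absent endpoint on an ordinal scale needs its threshold fixed before the scores are seen. Here the permission to look for the best threshold sits inside the endpoint's definition, and the endpoint is reported on the scans that would be searched.

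Two things are at stake. The detection rate of suspected distant disease is a named secondary objective with an exact interval, and that interval has its stated coverage only for a cut-off chosen without reference to the data. Sensitivity computed at a cut-off picked to perform well on the same patients is biased upward.

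The search also needs a truth value to optimise against. Pelvic tissue cannot supply one for bone, lung, viscera or extrapelvic nodes. Any biopsies of those sites would probably exist only where a lesion was already suspected.

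**Working it through.** **1. The plan's own figures.** The documents give no figure for the distant objective. The primary design in 13.3 (10 patients, continue on 6 or more agreements; 16 in total, success on 11 or more; 50% against 75%) was recomputed from exact binomials:

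- Early stopping under the null: P(X ≤ 5 | 10, 0.5) = 0.623 (stated 0.62).
- Type I error: 0.1012 (stated 0.101).
- Power: 0.79995 (stated 79.9%).
- 90% interval at 12/16: 0.516 to 0.910 (stated 0.52 to 0.91).

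These reproduce, and none uses the sentence at issue.

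**2. What one patient is worth.** 1/16 = 6.25 percentage points. The Clopper-Pearson 90% limits for x of 16 are the 5% point of Beta(x, 17 − x) and the 95% point of Beta(x + 1, 16 − x):

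| Positive scans | Rate | 90% CI |
|---|---|---|
| 0/16 | 0% | 0 to 17.1% |
| 1/16 | 6.25% | 0.3 to 26.4% |
| 2/16 | 12.5% | 2.3 to 34.4% |
| 3/16 | 18.75% | 5.3 to 41.7% |

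The width is ordinary imprecision at n = 16, and a fixed cut-off does not narrow it. What a search adds is freedom to choose among rows after seeing the scores.

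**3. How many distant cases there could be.** The documents give no prevalence, so a range is assumed. Expected cases = 16p; chance of none = (1 − p)^16.

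| Assumed p | Expected cases | Chance of none |
|---|---|---|
| 2% | 0.3 | 72% |
| 5% | 0.8 | 44% |
| 10% | 1.6 | 19% |
| 20% | 3.2 | 3% |

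These are true cases. Verified cases would be fewer, because no distant verification is scheduled. With none verified, neither sensitivity nor an optimal cut-off is defined.

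**4. Optimism in sensitivity if cases are verified (illustration).** Assumptions, none from the documents: all 16 patients are correctly classified; 2, 3 or 4 truly have distant disease; scores 0 to 4 occur with probability 35/25/20/12/8% whatever the truth; the cut-off is the one of four that maximises sensitivity + specificity − 1 (Youden).

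- Fixed cut-off of 3 or more: sensitivity = 12% + 8% = 0.20, Youden index 0.
- Searched cut-off: mean apparent sensitivity about 0.56, 0.52 and 0.50, and Youden index about 0.25, 0.21 and 0.18, for 2, 3 and 4 cases. The rule for breaking ties moves the sensitivities by up to about 0.05.

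The score carries no information, so the whole Youden index is artefact. A wider simulation used informative, moderate and useless scores at prevalences of 5, 10 and 20%, in runs with at least one case, all verified. Apparent sensitivity exceeded the true value at the chosen cut-off by about 17 to 30 points. For the informative score it was 0.84 to 0.89, against a true 0.61 to 0.67.

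**5. Direction of the detection rate.** In that wider simulation the rate at the searched cut-off was on average 4 to 14 points above the rate at a fixed 3 or more. It was higher in 28 to 52% of runs, lower in 19 to 36%, and equal in the rest. The direction in any one trial cannot be predicted.

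**6. What a fixed cut-off does not repair.** Even if every verified case is detected, the lower 90% limit for sensitivity is 0.05^(1/n): 5% with one case, 22% with two, 37% with three. The upper limit is 100% each time.

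**The case against.** The wording is permissive: the scale and the cut-off search are both introduced by may. The objective is secondary, in a pilot, with no success rule attached. Labelling the search exploratory would meet much of the concern without deleting anything. The simulation inputs are the reviewer's, and an uninformative score is the least favourable case. All of this stands. It limits how serious the point is and makes the simulated figures illustrative, but it does not supply the missing threshold: no other section names a positive score.

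Two stronger readings are tempting and should be resisted.

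- *That the detection rate would be inflated.* The objective is the rate of suspected disease, which has no true value to be inflated against, and a search can raise or lower the threshold (step 5). The documents support only that the rate is undefined until the cut-off is fixed.
- *That the primary result or its error rates are compromised.* The search option is written for the distant endpoint alone, and the figures in 13.3 reproduce without it. Section 13.1 does count distant disease as a positive scan and names no score, which is a reason to state the reading rule clearly. It does not show that the agreement rate will be tuned.

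**Conclusion.** The point holds in a limited form and should be corrected. The cut-off for distant metastasis is not pre-specified, the plan allows it to be optimised on the 16 scans being reported, and the scheduled procedures provide no distant reference from which an optimum could be soundly derived.

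The detection rate is therefore open to post hoc choice in either direction, at 6.25 points per patient, and its 90% exact interval does not have its nominal meaning after a search. Distant sensitivity is not estimable if no distant case is verified, which is more likely the lower the true prevalence. If some are verified, sensitivity at a searched cut-off is optimistic: about 0.50 to 0.56 against 0.20 for a useless score, and 17 to 30 points in the wider simulation. Those sizes rest on assumed score distributions, case counts or prevalences, complete verification and the Youden criterion. The qualitative conclusion does not depend on them.

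**What to change.** - In 13.6, remove the optimal cut-off from the endpoint definition, or label any search exploratory and attach no performance claim to it.
- State, before the first read, that a distant lesion is positive at a score of 3 (probably malignant) or 4 (definitely malignant), so that one such lesion makes the scan positive for distant disease. This threshold follows the scale's own labels but is a choice the study team must confirm.
- Reconcile the 3-5 range in 5.4.2 with the 0-4 scale.
- Report the suspected-distant detection rate with its 90% exact interval at the fixed cut-off. Tabulate the rates at 2 or more and at 4 descriptively.
- Report distant sensitivity only for lesions with biopsy results already available, and describe it as such, or drop it. If only scan-positive lesions are biopsied, missed disease is never observed, so the figure cannot be read as ordinary sensitivity.

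The cost is a few sentences in 13.6 and 5.4.2. The reported figure may be less favourable, and no data-driven cut-off is offered. Sample size, power and type I error do not change.
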